5 STUDY TREATMENTS

5.1 Description of Treatments

5.1.1 *CTAP101 Capsules Description*

Dosage form: Soft capsule
Dose strength: 30 mcg capsule
Product description: Blue oval soft capsules containing white to off-white to slightly blue waxy material; 30 capsules per bottle
Active component: Calcifediol, calcidiol, 25-hydroxyvitamin D₃
Non-active components: Paraffin wax, mineral oil, mono- and diglycerides, dehydrated alcohol, lauroyl polyoxylglycerides, butylated hydroxytoluene, hypromellose, modified starch, carageenan, sodium phosphate dibasic, sorbitol and sorbitan solution, FD&C Blue #1, titanium dioxide, medium chain triglycerides (coconut oil)
Storage conditions: 15°C to 30°C (59°F to 86°F); protect from light and heat

5.1.2 *Placebo Capsules Description*

Dosage form: Soft capsule
Dose strength: 0 mcg capsule
Product description: Blue oval soft capsules containing white to off-white to slightly blue waxy material; 30 capsules per bottle
Active component: None
Non-active components: Paraffin wax, mineral oil, mono- and diglycerides, dehydrated alcohol, lauroyl polyoxylglycerides, butylated hydroxytoluene, hypromellose, modified starch, carageenan, sodium phosphate dibasic, sorbitol and sorbitan solution, FD&C Blue #1, titanium dioxide, medium chain triglycerides (coconut oil)
Storage conditions: 15°C to 30°C (59°F to 86°F); protect from light and heat

5.2 Treatments Administered

Study drug should **NOT** be administered to individuals known to be allergic to any component of the drug. All subjects should be observed for allergic reaction following study drug administration. All allergic reactions will be documented as AEs in the source documents and the electronic case report forms (eCRF).

Study drug will be provided in white, round, wide-mouth, high-density polyethylene (HDPE) bottles with 28-mm white, polypropylene, child-resistant (push down and turn) caps with aluminum heat induction seal liners and contain 30 capsules per bottle. Each bottle will contain either active drug or a matching placebo.

Drug accountability will be performed throughout the treatment period ([Section 5.12 Storage and Accountability](#)). All procedures being performed during the course of this clinical study are

listed sequentially by visit in [Section 7 Study Activities](#) and may be found as a table in [Appendix 1 Schedule of Events](#).

5.3 Selection and Timing of Dose for Each Subject

Subjects in Cohort 1 will receive two capsules (CTAP101 Capsules and/or matching placebo capsules) every day at bedtime to achieve the targeted initial daily dose of 30 mcg of calcifediol (one CTAP101 Capsule plus one placebo capsule) or 0 mcg of calcifediol (two placebo capsules). Any food intake within 60 minutes of medication administration will also be recorded. At the end of 12 weeks of treatment, subjects assigned to active treatment will undergo upward dose titration to 60 mcg per day (two CTAP101 Capsules) provided that (a) plasma iPTH has not decreased by at least 30% from pretreatment baseline, (b) corrected serum calcium is <9.8 mg/dL, (c) serum phosphorus is \leq 5.5 mg/dL, and (d) serum total 25-hydroxyvitamin D is \leq 65 ng/mL. Subjects in Cohort 2 will receive a starting daily bedtime dose which will be determined on the basis of the interim analysis of data obtained in Cohort 1, and will undergo upward dose titration at the end of 12 weeks of treatment to a new daily dose that is two times higher than the starting dose, provided that (a) plasma iPTH has not decreased by at least 30% from pretreatment baseline, (b) corrected serum calcium is <9.8 mg/dL, (c) serum phosphorus is \leq 6.0 mg/dL and (d) serum total 25-hydroxyvitamin D is \leq 65 ng/mL.

In order to maintain blinding, subjects will receive periodic supplies of study drug in bottles of identical appearance, some labeled “Bottle 1” and some labeled “Bottle 2,” along with the same dosing instructions regardless of randomization group directing the subject to take one capsule from one bottle labeled “Bottle 1” and one bottle labeled “Bottle 2” every day at bedtime.

An unblinded medical monitor who will be part of the independent, unblinded DSMB will oversee study drug assignments and dose adjustments (see below) by IRS.

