Subjects in both cohorts will reduce the dose by one capsule per week, as necessary, and no more frequently than at biweekly intervals, in the event that any one of the following four criteria are met: plasma iPTH is confirmed to be <35 pg/mL (for subjects with stage 3 CKD) or <70 pg/mL (for subjects with stage 4 CKD), serum calcium (corrected) is confirmed to be >10.3 mg/dL, serum total 25-hydroxyvitamin D is confirmed to be >100 ng/mL, or serum phosphorus is confirmed to be >5.5 mg/dL (ages 12 to <18 years) or >6.0 mg/dL (ages 8 to <12 years), provided that the investigator has deemed the elevated serum phosphorus to be related to study drug administration and has taken appropriate and persistent actions to control serum phosphorus by initiating or adjusting any phosphate binder therapy.

Dose reductions will be accomplished by consistently omitting doses on a specific day of the week, as follows:

- First dose reduction: Dosing will be omitted on all Mondays (M).
- Second dose reduction: Dosing will be omitted on all M and Wednesdays (W)
- Third dose reduction: Dosing will be omitted on all M, W and Fridays (F)
- Fourth dose reduction: Dosing will be omitted on all M, W, F and Sundays (S)

Any subject who requires a further dose reduction will terminate dosing with study drugs and immediately commence the 6-week FU period.

Subjects on dose reduction will be allowed an unscheduled safety visit if deemed appropriate by the investigator to have FU blood sampling within 48 hours of any dose reduction.

A summary of the initial and reduced weekly dose levels, in mcg units, after each of the four possible dose reductions appears in the table below:

Daily (mcg)	Weekly (mcg)	Weekly Dose (mcg)			
		1 st Reduction	2 nd Reduction	3 rd Reduction	4 th Reduction
60	420	360	300	240	180
30	210	180	150	120	90
0	0	0	0	0	0

Subjects will suspend dosing if plasma iPTH is persistently <30 pg/mL (three consecutive visits) or serum calcium (corrected) is confirmed to be >11.0 mg/dL, and resume when iPTH is ≥ 35 pg/mL and serum calcium is <9.8 mg/dL at the next lower dose level.

Primary Efficacy Endpoint:

The primary estimand is the reduction of mean plasma iPTH by at least 30% from pre-treatment baseline. The primary efficacy endpoint is the proportion of subjects in the intent-to-treat (ITT) population (age 8 to <18 years) attaining a mean decrease in plasma iPTH of at least 30% from pre-treatment baseline compared to placebo during the EAP.

Primary Safety Endpoints:

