3 INVESTIGATIONAL PLAN

3.1 Overall Study Design and Plan

This is a phase 3, multi-center, randomized, double-blind, placebo-controlled study which will be conducted primarily or entirely within the US. The study will involve approximately 108 eligible subjects, balanced for gender and CKD stage, having ages of 8 to <18 years, SHPT, stage 3 or 4 CKD and VDI. Approximately 72 subjects having ages of 12 to <18 years will be enrolled initially (Cohort 1) and, after prior approval from the US FDA, another 36 subjects having ages of 8 to <12 years will be enrolled (Cohort 2). Subjects in both cohorts will be randomized in a 2:1 ratio into two treatment groups to receive a daily bedtime dosage of (a) CTAP101 Capsules, or (b) matching placebo for 26-weeks. Subjects in Cohort 1 who are assigned to treatment with CTAP101 Capsules will start dosing at 30 mcg/day (1 CTAP101 Capsule) and, at the end of 12-weeks of treatment, will undergo upward dose titration to 60 mcg per day (two CTAP101 Capsules) provided that (a) plasma iPTH has not decreased by at least 30% from pretreatment baseline, (b) serum calcium (corrected for albumin) is <9.8 mg/dL, (c) serum phosphorus is ≤5.5 mg/dL, and (d) serum total 25-hydroxyvitamin D is ≤65 ng/mL. The initial dosage in Cohort 2 will be determined based on an interim analysis of data obtained from Cohort 1, as described below. The efficacy of CTAP101 Capsules (compared to placebo) in treating SHPT will be assessed from multiple plasma iPTH and serum 25-hydroxyvitamin D levels obtained in the efficacy assessment period (EAP), defined as the last 6 weeks of the 26-week treatment period.

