3.2 Rationale for Study Design and Control Group

EirGen is developing CTAP101 Capsules for the treatment of SHPT in pediatric patients with stages 3 or 4 CKD and VDI. The active ingredient in CTAP101 Capsules is calcifediol, which is formulated as ER capsules for oral administration.

The present study is designed to compare the efficacy of CTAP101 Capsules to matching placebo with regard to reducing mean plasma iPTH levels by at least 30% from pre-treatment baseline in pediatric patients with stage 3 or 4 CKD and VDI. The study will also examine the safety and tolerability of CTAP101 Capsules compared to placebo. This adequate and well-controlled, randomized and double-blind study provides the best means to evaluate efficacy, safety and tolerability of CTAP101 Capsules because no therapy has yet been approved by the FDA to treat elevated iPTH levels associated with low serum total 25-hydroxyvitamin D levels in pediatric CKD patients. In other studies conducted in adult subjects with stage 3 or 4 CKD and SHPT, administration of placebo therapy for 26-weeks has not been shown to result in untoward effects [Coyne 2006; Coburn 2004]. However, since iPTH values >900 pg/mL have been associated with increased risk of fracture in hemodialysis patients [Jadoul 2006], subjects will be terminated from this study for confirmed iPTH levels >900 pg/mL.

The starting dose of 30 mcg per day is based on the results from two phase 3 studies (CTAP101-CL-3001 and CTAP101-CL-3002) conducted in adults with SHPT, stage 3 or 4 CKD and VDI. Data from these studies demonstrated that steady-state serum 25-hydroxyvitamin D₃ levels were reached after 12 weeks of treatment at daily doses of 30 or 60 mcg of CTAP101 Capsules. Accordingly, upward dose titration is not allowed in the present study until after 12 weeks, when subjects receiving the initial dose of CTAP101 Capsules have attained steady-state blood levels of serum total 25-hydroxyvitamin D. A 26-week treatment period was selected for this study to ensure that steady-state will be attained in subjects who undergo upward dose titration at the beginning of treatment week 13.

Previous PK analyses in adult CKD patients have determined that the $t_{1/2}$ of serum 25-hydroxyvitamin D₃ is approximately 30 days (CTAP101-CL-2008). Consequently, the post-dosing FU period of 6-weeks should be sufficient for determining the $t_{1/2}$ in pediatric patients.

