5.4 Dose Reduction Criteria

Subjects will reduce the dose through the IRS by one capsule per week, as necessary, and no more frequently than at biweekly intervals, in the event that any one of the following four criteria are met:

1. Two consecutive visits with plasma iPTH <35 pg/mL (for subjects with stage 3 CKD) or <70 pg/mL (for subjects with stage 4 CKD),
2. Two consecutive visits with serum calcium (corrected) >10.3 mg/dL,
3. Two consecutive visits with serum total 25-hydroxyvitamin D >100 ng/mL, or
4. Two consecutive visits with serum phosphorus >5.5 mg/dL (ages 12 to <18 years), or >6.0 mg/dL (ages 8 to <12 years) provided that the investigator has deemed the elevated serum phosphorus to be related to study drug administration and has taken appropriate and persistent actions to control serum phosphorus by initiating or adjusting any phosphate binder therapy.

Dose reductions will be accomplished by consistently omitting doses on a specific day of the week, as follows:

- First dose reduction: Dosing will be omitted on all M.
- Second dose reduction: Dosing will be omitted on all M and W
- Third dose reduction: Dosing will be omitted on all M, W and F

- Fourth dose reduction: Dosing will be omitted on all M, W, F and S

Any subject who requires a further dose reduction will terminate dosing with study drugs and commence the 6-week FU period.

Subjects on dose reduction will be allowed a safety visit if deemed appropriate by the investigator to have FU blood sampling within 48 hours of dose reduction.

A summary of the initial and reduced weekly dose levels, in mcg units, after each of the four possible dose reductions appears in the table below:

Daily (mcg)	Weekly					Dose (mcg)
	Weekly (mcg)	1 st Reduction	2 nd Reduction	3 rd Reduction	4 th Reduction	
60	420	360	300	240	180	
30	210	180	150	120	90	
0	0	0	0	0	0	

Subjects will suspend dosing if plasma iPTH is persistently <30 pg/mL (three consecutive visits) or serum calcium (corrected) is confirmed to be >11.0 mg/dL, and resume when iPTH is \geq 35 pg/mL (for subjects with stage 3 CKD) or \geq 70 pg/mL (for subjects with stage 4 CKD) and serum calcium is \leq 9.8 mg/dL at the next lower dose level.

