7.2 Treatment Period (Weeks 1-26)

7.2.1 Visits 4-10 (Days 8-71)

- May occur ± 3 days of scheduled day
- AE assessment
- Concomitant medications

- VS measurements
- Blood samples drawn for:
 - Chemistry (partial panel)
 - Plasma iPTH
 - Serum total 25-hydroxyvitamin D

7.2.2 *Visits 11-12 (Days 83-84)*

- Must occur on the scheduled days
- AE Assessment
- Concomitant medications
- VS measurements
- Blood samples drawn for all subjects at 0 (pre-dose), 6 and 12 hours and additionally, only for subjects assigned to intensive PK evaluation, at -2, 2, 4 and 8 hours after dosing on Day 83 for:
 - Chemistry (partial panel)
 - Serum 25-hydroxyvitamin D₃, [REDACTED]
- Blood samples drawn at 24 hours ±4 hours before dosing on Day 84 for:
 - Chemistry (partial panel)
 - Serum 25-hydroxyvitamin D₃, [REDACTED]

7.2.3 *Visit 13 (Day 85):*

- Must occur on the scheduled day
- Urine pregnancy (for females of childbearing potential)
- AE assessment
- Concomitant medications
- Urine pregnancy (only for females of childbearing potential)
- VS measurement
- Urine chemistry and urinalysis
- Blood samples drawn at 48 hours ±4 hours before dosing for:
 - Chemistry (full panel) and hematology
 - Plasma iPTH
 - Serum total 25-hydroxyvitamin D
 - Serum 25-hydroxyvitamin D₃, [REDACTED]
 - [REDACTED]
- Drug accountability
- Patient reported palatability and acceptability

- Dispense assigned bottles of study drug

7.2.4 *Visits 14-21 (Days 92-169)*

- May occur ± 3 days of scheduled day
- Visits 14 and 16 are required only for subjects who underwent upward dose titration at visit 13
- AE assessment
- Concomitant medications
- VS measurements
- Blood samples drawn for:
 - Chemistry (partial panel)
 - Plasma iPTH
 - Serum total 25-hydroxyvitamin D

7.2.5 *Visit 22 (Day 183):*

- Must occur on the scheduled day
- Urine pregnancy (only for females of childbearing potential)
- AE assessment
- Concomitant medications
- VS measurements
- Urine chemistry and urinalysis
- Blood samples drawn for:
 - Chemistry (full panel) and hematology
 - Plasma iPTH
 - Serum total 25-hydroxyvitamin D
 - Serum 25-hydroxyvitamin D₃, [REDACTED]
 - [REDACTED]
- Patient reported palatability and acceptability
- Drug accountability

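### The week-12 titration rule ignores dose suspension: a Cohort 1 child suspended for hypercalcemia who meets it is sent to 420 mcg/week by 5.3 and to 180 mcg/week by 5.4

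*Combined protocol and SAP*

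**What the plan says.** **Titration.** Section 5.3 says that at week 12 "subjects assigned to active treatment will undergo upward dose titration to 60 mcg per day (two CTAP101 Capsules) provided that" four conditions hold in Cohort 1: (a) iPTH has fallen by less than 30% from baseline, (b) corrected calcium is below 9.8 mg/dL, (c) phosphorus is at most 5.5 mg/dL, and (d) total 25-hydroxyvitamin D is at most 65 ng/mL. Section 3.1 has the same rule (active subjects "will undergo upward dose titration to 60 mcg per day (two CTAP101 Capsules) provided that (a) plasma iPTH has not decreased" by 30%, and so on), as does the Synopsis. Cohort 2 doubles its own starting dose. No condition refers to a current or past suspension.

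**Suspension and resumption.** Section 5.4 states: "Subjects will suspend dosing if plasma iPTH is persistently <30 pg/mL (three consecutive visits) or serum calcium (corrected) is confirmed to be >11.0 mg/dL". Under 5.4, dosing resumes at the next lower level once iPTH is at least 35 pg/mL (stage 3) or 70 pg/mL (stage 4) and calcium is 9.8 mg/dL or less. The Synopsis differs slightly (iPTH at least 35 for all, "and serum calcium is <9.8 mg/dL at the next lower dose level") but gives the same direction.

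**Reductions.** "Dose reductions will be accomplished by consistently omitting doses on a specific day of the week", up to four days a week, with a table of the resulting weekly doses.

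**The concern.** Both rules are written as mandatory, and they send the same child in opposite directions. The titration values are also a weak screen for this child, because stopping a drug that raises calcium and suppresses iPTH tends to lower calcium and let iPTH recover. That moves the child toward meeting conditions (a) and (b).

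Read literally, the plan doubles the starting daily dose of a child who became hypercalcemic on that starting dose, on the strength of calcium measured off drug or only just after restarting. Section 5.5 gives a half-life of about 30 days in adults with stage 3 or 4 CKD, says there is no specific antidote, and warns of calcification from repeated hypercalcemia. The issue is a child's safety, not bias in the primary comparison.

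**Working it through.** **1. The plan's own dose table (5.4).** Weekly dose = daily dose × (7 − days omitted).
- 60 mcg/day: 60 × 7, 6, 5, 4, 3 = 420, 360, 300, 240, 180.
- 30 mcg/day: 30 × 7, 6, 5, 4, 3 = 210, 180, 150, 120, 90.

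Both rows reproduce exactly.

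**2. Meeting titration implies meeting resumption.**
- Calcium: condition (b), below 9.8, satisfies both the 5.4 limit (9.8 or less) and the Synopsis limit (below 9.8).
- iPTH: condition (a) keeps iPTH above 0.70 × baseline. At the entry limits in 4.2 this is 0.70 × 100 = 70 pg/mL (stage 3) and 0.70 × 160 = 112 pg/mL (stage 4), against resumption limits of 35 and 70.
- Margin: the implication fails only for baselines below 35 / 0.70 = 50 (stage 3) or 70 / 0.70 = 100 pg/mL (stage 4), well under the entry limits that 7.1.3 asks to be confirmed at Visit 3.

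**3. Size of the conflict.**
- Cohort 1, suspended from the full 30 mcg/day: 5.3 gives 60 × 7 = 420; 5.4 gives 30 × 6 = 180. The gap is 240 mcg/week and the ratio 420 / 180 = 2.33.
- Cohort 2, starting dose d not yet set: (2d × 7) / (d × 6) = 14 / 6 = 2.33.

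**4. Why it arises at Visit 13.** Section 7.2.2 and the Schedule of Events show no iPTH draw at Visits 11 and 12. For a child still suspended after Day 71, the next scheduled visit with both iPTH and calcium is Visit 13 (Day 85), when titration is decided and, under 6.5, new bottles are assigned. There are two routes:
- *Same draw.* Calcium first falls below 9.8 on Day 85. Both rules then apply to that sample.
- *Two steps.* Calcium is also drawn at Visits 11 and 12 ("Blood samples drawn for all subjects at 0 (pre-dose), 6 and 12 hours" on Day 83, and again on Day 84). Section 5.4 does not require iPTH and calcium from one visit, so a child with adequate iPTH on Day 71 can resume at 180 mcg/week on Day 83 or 84 and then be titrated on Day 85. Even if the omitted day is kept, the dose becomes 60 × 6 = 360, twice the 180 just chosen for safety.

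**5. What limits the exposure.** "Visits 14 and 16 are required only for subjects who underwent upward dose titration at visit 13" (7.2.4). The first of these is Day 92, 92 − 85 = 7 days after titration. Calcium and phosphorus are not among the blinded results, and 5.4 continues to apply. However, a new calcium-driven reduction needs two consecutive visits, and Day 85 calcium was below 9.8, so Day 92 alone cannot trigger one. Going from 420 to 180 takes four reductions at least two weeks apart, so 3 × 2 = 6 weeks from first to fourth. A second suspension would resume at 360.

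**6. How many children.** Entry calcium is below 9.8, so exceeding 11.0 needs a rise of more than 11.0 − 9.8 = 1.2 mg/dL. The adult phase 3 mean rise was 0.2 mg/dL (1.13), one sixth of that. No SD of individual changes is given, so the number cannot be computed.

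**The case against.** **Section 5.4 is the specific rule and should win.** It addresses suspended subjects directly, while 5.3 is general. Section 3.2 explains that titration waits until week 12, "when subjects receiving the initial dose of CTAP101 Capsules have attained steady-state blood levels of serum total 25-hydroxyvitamin D", and a suspended child is not on the initial dose. This is the sensible reading. But 3.2 explains timing and sets no eligibility condition, and no sentence gives 5.4 precedence. Precedence would also not help the two-step child, who has already complied with 5.4 by Day 85.

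**The Day 83 and 84 draws remove most same-draw clashes.** If results return quickly, a strict clash needs calcium above the resumption limit on those days and below it on Day 85. That narrows the first route. It leaves the second, which has the same consequence. If results return slowly, Visit 13 must rely on earlier values, and step 2 of the working applies to those too.

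**Oversight exists.** The IRS makes each adjustment and the unblinded Data Safety Monitoring Board (DSMB) monitor verifies it. The IRS logic and DSMB charter are not in the documents and may already settle the matter, so a failure in operation cannot be shown. But verification needs a rule to verify against, and sites are blinded to iPTH and 25-hydroxyvitamin D (5.7), so they cannot apply the titration test themselves.

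**A stronger reading that does not hold.** A reader might infer that a child already on reduced dosing regains the omitted days on titration, going from 180, 150, 120 or 90 to 420 mcg/week (2.3-, 2.8-, 3.5- or 4.7-fold). No text restores omitted days at titration. The 5.4 table gives the 60 mcg/day row its own reduced levels, so carry-over is implied: 180 to 360, 150 to 300, 120 to 240, 90 to 180, each 2.0-fold. Stating it would be an optional clarification; its absence is not a separate error.

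**Conclusion.** The point holds for suspended children. The written rules direct 420 mcg/week and 180 mcg/week for the same Cohort 1 child, or allow titration a day or two after a cautious restart, and nothing says which prevails.

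The 180 assumes suspension from the full 30 mcg/day with no earlier reduction. Confirmed calcium above 11.0 also meets the 10.3 reduction criterion, so a strict reader might arrive at 150, which widens the gap. The overlap of the two sets of limits assumes that baseline iPTH is at least 50 (stage 3) or 100 pg/mL (stage 4).

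A reader might also infer that many children are at risk or that the IRS would actually dose this way. The documents support neither: the required calcium rise is large against the adult mean, and the IRS logic is not shown. This is a gap that should be closed because closing it is cheap and protects a child. It is not a flaw that undermines the trial.

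**What to change.** Add to 5.3, 3.1 and the Synopsis (Study Design and Dosing Plan), and build into the IRS logic: *A subject whose dosing is suspended at Visit 13, or was suspended at any time since Visit 10 (Day 71), is not titrated at Visit 13 and follows 5.4, resuming at the next lower level of the starting dose once the resumption criteria are met.* Give the same text to the DSMB's unblinded monitor. Day 71 is the natural cut-off because it is the last scheduled visit before Visit 13 with both iPTH and calcium.

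Optionally, add that omitted days carry over to the titrated dose. Whether a child with an earlier, resolved calcium problem should be titrated at all is for the sponsor's clinical judgment.

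Cost: one sentence in each place and one IRS check. Titration is offered only at week 12, so the few children affected would not be titrated later and may be less likely to reach the 30% iPTH response.
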